An emerging aquatic plant protein introduced to the Western diet is from the duckweed family(11,12), *Wolffia*, a genus within the duckweed family, has been characterized as a rich source of certain EAA compared to seeds(13). Moreover, *Wolffia* has a long history in Southeast Asia as a natural food source or "vegetable meat ball"(12). The morphological structure of *Wolffia globosa* (14,15) is a simple, rootless thalus 0.4-0.9 mm long (the smallest plant on earth), without veins, having a budding pouch at its basal end. Clonal clusters are arranged either solitary or two connected, consisting of a mother plant and a daughter plant. The nutritional properties of Mankai, a cultivated strain of *Wolffia Globosa*, is reflected in high protein content (more than 45%) of the dry matter, the presence of 9 essential and 6 conditional AAs and demonstrable protein digestibility corrected amino acid score [PDCAAS] of 89%.

Main objective

We aim to explore the EAAs bioavailability of Mankai intake in healthy humans, compared to intake of iso-protein containing meals of well-established animal (soft cheese) and plant (peas) protein sources.

Experimental design

Three days prior to the test meal, the participants will be instructed to maintain a stable diet that consist of detailed recipes tailored to provide 2,000 kcal/day, comprised of 55% carbohydrates, 15% protein, and 30% fat from total energy.

Baseline blood samples will be taken after a 12h overnight fast by four paramedics and, following meal administration, after 30, 90 and 180 minutes. To keep exact timeintervals, each randomized intervention group will be further divided into three time groups, with baseline sampling at 8 am, 8.15 am, 8.30 am, and the exact time sequence will be maintained throughout the entire study. This study is a single-phasetrial.

Each test meal will provide 30 gr of protein from the respective source: 1. Cheese protein (333gr of soft white cheese, 9% fat) 2. Green peas (cooked, cutlet) 3.

Wolffiaglobosa (Mankai, cooked, cutlet). A chef prepared the cutlets that included 30gr protein from either peas (600gr) or Mankai (410gr) with an additional minimal list of ingredients. The final recipe included the following additional ingredients for both cutlets: onions (280 gr), mushrooms (200 gr), canola oil (21gr for peas, 58.2gr for Mankai), protein-free stabilizer (16.2gr for peas, 13.4gr for Mankai), salt and pepper. The cheese meal will include one slice of bread. In addition to the 30gr equivalent protein content of each protein specific source, the estimated amount of protein provided in each dish will be as follows: cheese (39.7gr), peas (39.3gr) and Mankai (39.3gr). While other nutritional values/components varied across groups, the 3 test meals groups have

a complete profile of all the 9 EAAs.

All the test meals will be served with a 250ml bottle of mineral water. To maintain an exact time frame, the participants will be required to complete their meal within 15 minutes at their allocated food tables. Blood samples will be taken at baseline, and at 30, 90, and 180 minutes post administration of the test meals for the EAAs measurements. Other parameters will be measured only in 3 hours interval.

Statistical analysis plan

The primary outcome is the change of the EAAs concentration in the blood. The secondary outcomes are selected blood biomarkers, as B12 vitamin, which is primarily derived by animal protein sources. Computer-generated random numbers will be used to assign the subjects to the three different meals randomly. All the statistical analyses will be based on non-parametric tests. Differences in blood measures at various time points, as compared to baseline, will be analyzed by the Friedman or Wilcoxon test, depending on the number of time points. To examine the differences between the three meal groups, we will use the Kruskal-Wallis test. In case of significant differences between groups, we will use Mann-Whitney test as a post-hoc test. In a sensitivity analysis, the data will be further tested by using general estimating equation (GEE) model with a random effect for subjects and fixed effect of meal groups. Statistical analyses will be performed with IBM SPSS (version 24). All *P*-values are two-sided, and $P < 0.05$ is considered statistically significant.

References

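### The plan does not fix which EAA result is primary and calls every P<0.05 significant, so the chance of a false meal difference runs from about 5% to well above it

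*Combined protocol and SAP*

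**What the plan says.** The primary outcome is defined in one sentence of the Statistical analysis plan: "The primary outcome is the change of the EAAs concentration in the blood". The Experimental design section supplies the dimensions. The meals are said to have "a complete profile of all the 9 EAAs", and the sampling scheme reads: "Blood samples will be taken at baseline, and at 30, 90, and 180 minutes post administration of the test meals for the EAAs measurements".

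Three testing steps follow in the Statistical analysis plan:

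- Within meals: "Differences in blood measures at various time points, as compared to baseline, will be analyzed by the Friedman or Wilcoxon test".
- Between meals: "To examine the differences between the three meal groups, we will use the Kruskal-Wallis test".
- Pairs: "In case of significant differences between groups, we will use Mann-Whitney test as a post-hoc test".

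The sensitivity analysis is a "general estimating equation (GEE) model with a random effect for subjects and fixed effect of meal groups". The threshold is common to everything: "All *P*-values are two-sided, and $P < 0.05$ is considered statistically significant". No correction or order of testing is given.

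**The concern.** The sentence on Kruskal-Wallis testing names no EAA and no time. The following analyses would all comply with the text:

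- 27 tests: each EAA at each time.
- Nine tests: each EAA at one time or on one summary.
- Three tests: the total at each time.
- One test: the total at one time or as one summary.

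The choice can be made after the data are seen. A chance result on any EAA at any time could then be reported as the primary difference between Mankai and cheese or peas without departing from the plan.

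The plan also does not say that the between-meal test, rather than the within-meal test, is the primary one. That is a smaller labelling gap.

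**Working it through.** **Inputs from the documents.** Three meal groups; three post-baseline times (30, 90, 180 minutes); two-sided 0.05 per test. Nine EAAs is taken from the description of the meals, on the reading that all nine are assayed.

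**Inputs assumed.** Group size (8, 12 or 20 per arm) and the correlations between EAAs and between times (0 to 0.95). The text available for review gives neither. Changes from baseline are simulated as normal with equal variance. Kruskal-Wallis uses the chi-square reference with 2 degrees of freedom.

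**The plan's own figure.** One Kruskal-Wallis test in simulation gives 4.7-5.0%, so the stated 0.05 is reproduced for a single test.

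**Independence formula**, 1 - 0.95^k:

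- k = 3: 1 - 0.95^3 = 0.143
- k = 9: 1 - 0.95^9 = 0.370
- k = 27: 1 - 0.95^27 = 0.750

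**Simulation, identical meals**, 10,000 replicates, chance of at least one significant Kruskal-Wallis test:

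| Reading | Simulated range | Formula |
|---|---|---|
| One total area | 4.2-5.0% | 5% |
| Total at three times | 7.2-13.7% | 14.3% |
| Nine EAAs, one time | 10.3-36.3% | 37.0% |
| Nine EAAs, three times | 15.2-73.9% | 75.0% |

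For the 27-test reading, by correlation between EAAs / between times: 0/0, 72-74%; 0/0.5, 68-70%; 0.5/0.5, 56-57%; 0.8/0.7, 34-36%; 0.9/0.9, 21-23%; 0.95/0.95, 15%. Changes that share one baseline value are unlikely to be uncorrelated over time, so the very top of the range is the least plausible part. Correlation above 0.95 would go lower still.

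**What the Kruskal-Wallis gate does.** Within one variable, the gated Mann-Whitney step holds the pairwise error at 4.8% with all meals equal and 4.9-5.4% with one meal different. Without the gate, and with all meals equal, it is 12-13%. The three pairs therefore add nothing to the inflation above.

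**Only cheese differs** (by 1 or 2 SD, 12 per arm, Mankai and peas equal). The chance of a false Mankai-pea difference after the gate is 16-77% for 27 tests, 11-40% for nine, 8-15% for the total at three times and 5-6% for one total. The tops depend on the approximation. At 12 per arm the uncorrected normal approximation to Mann-Whitney has true size 5.19%, and the exact test 4.49%. For 27 independent tests:

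- approximate: 1 - (1 - 0.0519)^27 = 0.76
- exact: 1 - (1 - 0.0449)^27 = 0.71

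The approximation has size 4.99% at 8 per arm and 4.91% at 20, so the excess over 75% is particular to the group size assumed.

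**The case against.** - **The study is exploratory.** The Main objective is worded as an exploration, and this is a single-meal study. That lowers the consequence and may make a labelling change sufficient. It does not settle the matter, because the plan still names a primary outcome and a significance threshold and does not label its results exploratory.
- **The meals differ, so identical responses are irrelevant.** The Experimental design section does say that other components varied. But with cheese alone different, a false Mankai-pea difference is about as likely.
- **EAAs move together.** Probably so, and the low ends reflect it. At correlation 0.95 in both directions, 27 tests still give about 15%.
- **The GEE handles repeated measures.** It is a sensitivity analysis and names no outcome and no time term, so it cannot define the primary quantity.

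Two stronger readings are tempting and are not supported. A reader might infer that any reading with more than one test multiplies the error several-fold. It does not: the total at three times gives 7-14%, and nine tests at correlation 0.95 give about 10%, twice nominal. A reader might also infer that a rise from baseline within one meal could serve as the primary result. The Main objective is explicitly a comparison with cheese and peas, and the plan assigns Kruskal-Wallis to meal differences, so a within-meal rise would not answer it. What remains there is a missing label.

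**Conclusion.** The concern holds and should be settled before analysis. The primary quantity is not fixed, and no rule controls error across EAAs or times. The resulting chance of a false meal difference is about 5% on the narrowest reading and 15-75% on the widest, with about 56% in the middle case of correlation 0.5. These sizes rest on assumed correlations, group sizes and normal changes. Group size has little effect on the identical-meals figures; correlation has a large one. The documents do not support quoting any single figure as the trial's error rate.

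**What to change.** Choose one option according to the question of main interest, and write it into the plan before analysis.

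**A. Overall EAA response.** Use the baseline-corrected 0-180 minute area of total EAAs (sum of the nine in molar units). With d the change from baseline, the trapezoid rule gives 30/2·d30 + 60/2·(d30 + d90) + 90/2·(d90 + d180) = 45·d30 + 75·d90 + 45·d180. Total EAA change at one named time would serve equally to remove the ambiguity. Use one Kruskal-Wallis test at 0.05, with Mann-Whitney pairs at 0.05 only if it is significant.

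**B. EAA-specific response.** Use nine EAA areas, with Kruskal-Wallis and the gated Mann-Whitney pairs both at 0.05/9 = 0.0056. With three groups the gate holds each EAA at 0.05/9, and 9 × 0.05/9 = 0.05. Simulated error for any false pair, with cheese shifted 2 SD on three, five or nine EAAs, was 1.4-3.1%.

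**C. No confirmatory claim.** Say so, report all EAAs and times with estimates, and label the unadjusted P-values exploratory.

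Under A or B, label the other EAA and single-time results and the within-meal Friedman/Wilcoxon tests secondary or exploratory. If an area is used, state how a missing sample is handled, including a missing 180-minute one, which interpolation cannot fill.

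**Costs.** Wording only; no new samples. Fewer individual results will count as significant, and an area gives up timing in the confirmatory test. C gives up any confirmatory claim. The choice between A and B is a real trade-off. Simulated power for a Mankai-pea difference (assumed 12 per arm, Mankai alone shifted, EAA correlation 0.5 to 0.8):

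| Areas that differ | A | B |
|---|---|---|
| All nine, 1 SD | 83% at 0.5, 65% at 0.8 | 60% at 0.5, 44% at 0.8 |
| Two, 1.5 SD, same direction | 8-12% | 70-77% |
| Three, 1 SD, same direction | 8-12% | 31-40% |
| Two, 1.5 SD, opposite directions | about 3% | 89-91% |

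A is the stronger choice if the EAAs are expected to shift together. It has little power if only a few differ, whatever their direction.

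### The main between-meal analysis names no estimate or interval for Mankai versus cheese or Mankai versus peas, and tests pairs only after a significant Kruskal-Wallis test

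*Combined protocol and SAP*

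**What the plan says.** Under Main objective, the combined protocol and SAP states: "We aim to explore the EAAs bioavailability of Mankai intake in healthy humans, compared to intake of iso-protein containing meals". The reference foods it goes on to name are soft cheese and peas.

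Under Statistical analysis plan:

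- Outcome: "The primary outcome is the change of the EAAs concentration in the blood".
- General approach: "All the statistical analyses will be based on non-parametric tests".
- Between-meal comparison: "To examine the differences between the three meal groups, we will use the Kruskal-Wallis test".
- Pairwise step: "In case of significant differences between groups, we will use Mann-Whitney test as a post-hoc test".
- Sensitivity analysis: "In a sensitivity analysis, the data will be further tested by using general estimating equation (GEE) model". It has a fixed effect for meal group and does not depend on the Kruskal-Wallis result.
- Significance: two-sided P values against 0.05.

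The documents name no reference meal, Mankai contrast, between-meal effect measure or confidence interval.

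**The concern.** Kruskal-Wallis asks whether any of the three meals differ. That answers neither question in the objective. Under the plan's own rule, the pairwise question is asked only if the global test is significant, and then through Mann-Whitney tests for which no accompanying effect size is planned.

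The study sets out to explore bioavailability. Its useful result is how far Mankai lies from each reference food and how uncertain that distance is. If the plan is followed as written and the global test is null, the reader gets no main-analysis figure for Mankai against cheese or against peas. The reader then cannot tell a small difference from one that the trial was too imprecise to show. A null P value reported alone is also easily taken for similarity.

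**Working it through.** The documents supplied give no sample size, SD or effect size, so there is no figure to reproduce. The core of the check is a reading of the text; the arithmetic covers the gate and the cost of the fix.

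**1. What the plan provides for each Mankai contrast**

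| Kruskal-Wallis result | Main analysis | GEE sensitivity analysis |
|---|---|---|
| Significant | Mann-Whitney tests; no estimate or interval named | Runs; no contrast, estimate or interval named |
| Not significant | Nothing pairwise | Runs; no contrast, estimate or interval named |

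No cell contains a planned estimate. The lower main-analysis cell contains no pairwise result at all.

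**2. Is the gate itself an error?** Simulation with 3,000 runs per setting, normal data with SD 1, one EAA at one time, and assumed n of 8, 12 and 20 per meal.

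- All meals equal: the chance of any false pairwise finding with the gate was 0.042, 0.044 and 0.052. Two ungated, unadjusted Mankai contrasts gave 0.089, 0.082 and 0.087 (if independent, 1 − 0.95² = 0.0975).
- Mankai 1 SD from cheese, peas midway: the chance of declaring Mankai and cheese different was 0.30, 0.49 and 0.77 with the gate. It was 0.43, 0.61 and 0.85 ungated at 0.05, and 0.28, 0.47 and 0.77 with the two Mankai contrasts each tested at 0.025.

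For one endpoint the gate holds the error rate near 0.05, and in this scenario it loses nothing against an ungated pair of contrasts tested at a split alpha. There is no case here for removing it.

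**3. Size of the added table.** The Experimental design section gives 9 EAAs and post-meal samples at 30, 90 and 180 minutes. If each EAA is analysed at each time, there are 9 × 3 = 27 endpoints and 27 × 2 = 54 contrast rows.

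**4. How often would intervals and the gate disagree if all meals were equal?** Assumed: 12 per arm, normal data, 27 endpoints. The Hodges-Lehmann 95% CI runs from the k-th smallest to the k-th largest of the 12 × 12 = 144 pairwise differences, with

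k = 144/2 − 1.96 × √(144 × 25/12) = 72 − 1.96 × 17.32 = 38.05, taken as 38.

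- For one endpoint, the chance that Kruskal-Wallis is null while at least one of the two Mankai intervals excludes zero is about 0.043.
- Expected number over the table: 27 × 0.043 = 1.16. The simulations gave about 1.1 to 1.2.
- Chance of at least one if endpoints are independent: 1 − (1 − 0.043)²⁷ = 1 − 0.305 = 0.695.
- Simulated chance of at least one, across separate runs: 67-70% at between-endpoint correlation 0, 55-59% at 0.5, and 37-39% at 0.8.

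**5. A figure that carries no weight.** One can ask how often, after a null Kruskal-Wallis test with no true difference, the Mankai-cheese interval would still include a 0.8 SD deficit. The answer runs from about 75% (8 per arm, normal data) to about 1% (30 per arm, log-normal data). N, SD, distribution and the 0.8 SD mark are all assumed, so the conclusion does not use it.

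**The case against.** **The plan does not say it will report only P values.** This stands. The section is one paragraph on tests and a threshold, with no reporting section. A reader might infer a decision to withhold effect sizes, but the text is merely silent and does not forbid intervals. The point is that none is planned.

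**The GEE covers the gap.** This stands in part. A three-level meal effect normally yields coefficients and standard errors from which both contrasts follow, and the model is not conditional on Kruskal-Wallis. So a null global test does not leave the trial without any means of estimating them. But the plan presents the GEE as further testing, in a sensitivity role, and commits to no contrast, estimate or interval.

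**The gate is good practice.** This stands for a single endpoint, as step 2 shows. A reader might infer a type I error fault; the documents and the check do not support that.

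**No claim of similarity is made.** This also stands. The aim is exploratory and the documents claim no comparability. Misreading a null result is a risk of reporting, not something the plan proposes.

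**Hodges-Lehmann is one choice among several**, and is easiest to interpret when the meals differ by a shift in location. This is fair. It suits the plan's rank-based approach, but another prespecified estimate with an interval would also meet the point.

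**Ungated intervals bring their own confusion.** This stands, and step 4 gives its size. It is a reason to label the intervals and keep the gate, not a reason to leave the contrasts unestimated.

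**Conclusion.** The concern holds in a limited form. The main analysis has no planned estimate or interval for either comparison in the objective, and after a null Kruskal-Wallis test it has no planned pairwise result at all. This rests on the text alone and needs no assumption about sample size or variability.

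The tests are valid, data collection is unaffected, and no planned conclusion is shown to be wrong. The table-level disagreement rate of roughly 40-70% is a cost of the remedy and not a measure of the defect. It depends on the assumed 12 per arm, normal data, 27 separately analysed endpoints and correlations from 0.8 down to 0. Overall this is a cheap improvement worth making.

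**What to change.** 1. Name Mankai minus cheese and Mankai minus peas as the two planned contrasts for change in EAA concentration from baseline.
2. Report the Hodges-Lehmann shift with 95% CI for both, whatever the Kruskal-Wallis result. Label the intervals descriptive and not adjusted for multiplicity.
3. Keep the existing gate for any claim of significance. Where Kruskal-Wallis is null but an interval excludes zero, report the interval as it stands and claim no significant difference.
4. Word a non-significant result as 'difference not established', never as similarity.

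The cost is a few sentences in the statistical analysis plan and one table, of 54 rows at most if every EAA is analysed at every post-meal time. No new data are needed.

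There are two downsides. Wide intervals will show some null results to be inconclusive. And about one endpoint per trial (1.1 to 1.2 under the assumptions above) will show an interval excluding zero beside a null global test even when the meals are equal. Items 2 and 3 should therefore be adopted together.

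### The GEE sensitivity analysis contradicts itself, leaves its response undefined, and with meal as the only named fixed effect neither adjusts for baseline nor can test whether the time course differs by meal

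*Combined protocol and SAP*

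**What the plan says.** One sentence in the Statistical analysis plan section defines the sensitivity analysis. It begins "In a sensitivity analysis, the data will be further tested by using general estimating equation (GEE) model" and describes the model as a "general estimating equation (GEE) model with a random effect for subjects and fixed effect of meal groups". Nothing else in the combined protocol and SAP gives the response, a baseline covariate, a time or meal-by-time term, the working correlation or the type of standard error.

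The surrounding text:

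- Outcome: "The primary outcome is the change of the EAAs concentration in the blood". No time point or summary measure is named.
- Sampling for the essential amino acids (Experimental design): "Blood samples will be taken at baseline, and at 30, 90, and 180 minutes post administration of the test meals".
- Sampling for everything else (Experimental design): "Other parameters will be measured only in 3 hours interval", read here as baseline and 3 hours.
- Main tests: "All the statistical analyses will be based on non-parametric tests", and between meals "To examine the differences between the three meal groups, we will use the Kruskal-Wallis test", with Mann-Whitney tests post hoc. Friedman or Wilcoxon tests compare time points with baseline.
- Software: IBM SPSS version 24.

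**The concern.** There are three problems.

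1. **The model as written does not exist.** A subject random effect belongs to a mixed model, and a GEE has none. An analyst must drop half of the sentence, and the plan does not say which half.
2. **The response is open.** It could be all four raw concentrations, the three changes from baseline, or the three post-meal concentrations. It is also unclear whether the model covers the secondary biomarkers, which follow a different sampling schedule.
3. **Meal is the only fixed effect named.** Such a model estimates one time-averaged mean per meal. It has no parameter for a difference in time course, and baseline does not enter as a covariate.

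At stake are the clarity and precision of a supporting analysis. The rank tests between meals take no covariate, so no planned analysis adjusts for baseline in that way. Different analysts could fit different models, with different precision, under the same sentence. The standard error is also unspecified, and that choice affects the false-positive rate when arms are small.

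**Working it through.** The plan states no sample size, SD, correlation or power, so there is no figure of its own to reproduce. From the documents come three meals, samples at 0, 30, 90 and 180 minutes, and two-sided 0.05. Everything else below is assumed.

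**Precision.** With balanced data each model reduces to one value per subject. Take unit SD, baseline-to-post correlation a, post-to-post correlation c, and a sustained meal difference d at all three post-meal times. Variance divided by squared effect (in units of d) is:

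- four raw values: the variance of the mean is (4+6a+6c)/16 and the effect is 0.75d, because the pre-meal sample is averaged in. This gives (4+6a+6c)/9;
- mean change: (1+2c)/3 + 1 − 2a;
- post-meal mean: (1+2c)/3;
- baseline-adjusted post-meal mean: (1+2c)/3 − a².

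Example, a = c = 0.5: 10/9 = 1.111; 0.667; 0.667; 0.667 − 0.25 = 0.417. Dividing by the last gives 2.67, 1.60 and 1.60 times the subjects.

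| a, c | Raw (4) | Change | Post-meal only |
|---|---|---|---|
| 0.3, 0.3 | 1.90 | 2.11 | 1.20 |
| 0.5, 0.5 | 2.67 | 1.60 | 1.60 |
| 0.7, 0.7 | 4.44 | 1.29 | 2.58 |
| 0.2, 0.7 | 1.37 | 1.84 | 1.05 |
| 0.3, 0.7 | 1.56 | 1.69 | 1.13 |
| 0.5, 0.85 | 2.07 | 1.38 | 1.38 |

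The excess over the adjusted variance is (a+1/3)² for raw, (1−a)² for change and a² for post-meal only, whatever c is. None of the three beats adjustment, apart from the one degree of freedom it costs. Post-meal only is better than change below a = 0.5 and worse above it.

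**Power illustration.** Assume 12 per arm and a sustained 1-SD difference in one arm, with F tests on subject means and 20,000 replicates. Power for raw/change/post-only/adjusted is 62/85/85/97% at a = c = 0.5, and 65/52/78/78% at a = 0.2, c = 0.7.

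**Time course.** Assume 30 per arm, correlation 0.6 and 400 runs, with profiles that cross but have equal averages. The meal-only GEE rejected in 6.8% of runs, close to its null rate of 5.3–5.5%. A meal-by-time test rejected in 100%.

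**Type I error.** F tests on subject means rejected a true null in 4.7–5.3% of runs on all three readings and with adjustment. A meal-only GEE on the post-meal values, with an uncorrected robust Wald chi-square and correlation 0.5, rejected in 11.3, 9.3, 7.4 and 6.3% at an assumed 8, 12, 20 and 30 per arm. Adding baseline does not cure this: 14.3, 10.2, 7.4 and 6.6%.

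**Covariance in a mixed model.** A random intercept alone treats all post-meal pairs as equally correlated. At 12 per arm, under assumed unequal correlations or SDs, the meal-by-time test then rejected a true null in about 7 to 8.5% of runs, against 5.1% when they were equal. The average meal contrast was not affected.

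**The case against.** The strongest reply is that this is a sensitivity analysis, that the firm defect is a single sentence, and that covariate adjustment is a gain in efficiency rather than the correction of an error. No meal-by-time objective is stated; the Main objective concerns bioavailability. The authors may also have meant more terms than they wrote. Most of this stands, and it limits the severity. It does not rescue the sentence: a GEE with a subject random effect cannot be fitted as described, and terms that are not written are not specified.

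A reader might infer more than the documents support:

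- *That the main comparison of meals is compromised.* It is not. The Kruskal-Wallis and Mann-Whitney tests do not depend on this model.
- *That this model is the only place where baseline or the combined post-meal samples could be used.* Rank tests on change use baseline, and a rank test on a mean change or incremental area would combine the samples. The plan neither specifies nor excludes these. Only adjustment for baseline as a covariate is absent.
- *That a sustained effect will be diluted to three quarters, or that 4.4 times the subjects are needed.* Both require the pre-meal sample to be part of the response. The stated outcome is change, for which there is no dilution and the multiples are 1.3 to 2.1.
- *That the false-positive rate is certainly kept, or certainly inflated.* It is kept for F-type tests and inflated for an uncorrected robust Wald test in small arms. The plan gives neither the standard error nor the arm size.

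**Conclusion.** The point holds as a defect of specification and precision in a supporting analysis. The contradiction, the undefined response, the missing baseline covariate and the lack of any time-course test follow from the text alone.

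The sizes do not. They assume normal data, balanced arms, a sustained difference, equal SDs and the correlations in the table. Under those assumptions the loss against baseline adjustment runs from 5% (post-meal values, weak baseline correlation) to more than fourfold (all four raw values, correlation 0.7). The false-positive rate of about 9% also assumes 12 per arm and an uncorrected robust test. Severity is minor to moderate.

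**What to change.** Replace the sentence with:

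> In a sensitivity analysis, for each EAA, a linear mixed model (SPSS MIXED) will be fitted to the 30, 90 and 180 minute concentrations, with fixed effects for baseline concentration, meal, categorical time and meal-by-time, and an unstructured within-subject covariance. The main contrast is the baseline-adjusted average post-meal difference between meals; the meal-by-time test is supportive. Biomarkers with one post-meal sample will be analysed by a linear model of the 3-hour value on baseline and meal.

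The unstructured covariance avoids assuming that samples at 30, 90 and 180 minutes are all equally correlated. Its own small-sample error rate was not simulated here.

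If GEE is kept, delete the random-effect phrase, state the response and working correlation, use the same fixed effects, and specify a model-based or small-sample-corrected standard error.

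The cost is SAP wording and slightly more analysis work, with no extra samples. The mixed model is parametric, so residuals need checking, with a log scale if they are skewed. The rank tests stay as planned.

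### None of the between-meal analyses, including the sensitivity GEE, adjusts for the participant's fasting EAA value as a covariate

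*Combined protocol and SAP*

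**What the plan says.** The Statistical analysis plan states: "The primary outcome is the change of the EAAs concentration in the blood". Under Experimental design, EAAs are sampled after the overnight fast and at 30, 90 and 180 minutes, so every participant has a baseline value.

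Three between-meal analyses are planned:

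- The main test is set out as follows: "To examine the differences between the three meal groups, we will use the Kruskal-Wallis test".
- If that overall test is significant, pairs of meals are compared by Mann-Whitney.
- As a sensitivity check, the plan adds a "general estimating equation (GEE) model with a random effect for subjects and fixed effect of meal groups".

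No baseline, time or meal-by-time term is listed for the last of these. Baseline is named explicitly only in the within-person Friedman or Wilcoxon comparisons, which do not compare meals. The plan does not say whether the between-meal tests and the GEE take changes, post-meal values or all four values as the response.

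**The concern.** The GEE is the one planned between-meal model that could carry a covariate, and it omits the most obvious one. Because the primary outcome is a change, baseline is probably subtracted, which fixes its slope at 1. That is an inference from the outcome definition. If the true slope differs from 1, change stays correlated with baseline: the meal contrast is noisier than it need be, and a chance imbalance in fasting EAA is only partly corrected.

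If the GEE uses all four values as responses with meal as its only fixed effect, there is a further problem. The fasting value, which the meal cannot affect, is averaged into the meal coefficient and dilutes it.

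Bias on average and inflated type I error are not at issue. Allocation is random, and Mann-Whitney runs only after a significant Kruskal-Wallis.

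**Working it through.** The plan has no figure on this point to reproduce.

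**Assumed inputs.** 12 participants per arm; normal data; correlation ρ between baseline and each post-meal value of 0.3, 0.5 or 0.7; correlation of 0.7 between post-meal values; ratio k of post-meal to baseline SD of 1, 1.5 or 2; one arm shifted by 1 post-meal SD; two-sided 0.05.

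**Variances.** For the mean of the three post-meal values, in baseline-SD units, let V = k²(1 + 2 × 0.7)/3 = 0.8k² and c = ρk, the slope on baseline. The per-participant variance behind a meal contrast is then:

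- post-meal values: V
- change: 1 + V − 2c
- baseline-adjusted, common slope: V − c²
- all four values, rescaled to the same effect: V + (1 + 6c)/9

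Change minus adjusted is (1 − c)², which is zero only when the slope is 1. Post-meal minus adjusted is c².

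**Change versus adjusted.** Power is for the time-averaged contrast of the shifted arm with another arm.

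| k | ρ | Change | Adjusted | Variance cut | Power, change | Power, adjusted |
|---|---|---|---|---|---|---|
| 1 | 0.3 | 1.20 | 0.71 | 41% | 59% | 79% |
| 1 | 0.5 | 0.80 | 0.55 | 31% | 76% | 88% |
| 1 | 0.7 | 0.40 | 0.31 | 22.5% | 96% | 99% |
| 1.5 | 0.3 | 1.90 | 1.60 | 16% | 74% | 79% |
| 1.5 | 0.5 | 1.30 | 1.24 | 5% | 88% | 88% |
| 1.5 | 0.7 | 0.70 | 0.70 | 0% | 99% | 99% |
| 2 | 0.3 | 3.00 | 2.84 | 5% | 78% | 79% |
| 2 | 0.5 | 2.20 | 2.20 | 0% | 89% | 88% |
| 2 | 0.7 | 1.40 | 1.24 | 11% | 98% | 99% |

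With complete data, an exchangeable GEE gives the same time-averaged contrast and robust standard error as least squares on participant means. Power was therefore simulated with model-based t tests on those means (20,000 replicates per cell), not with sandwich Wald tests. The gain ranges from −3 to +18 points at 8 per arm and from 0 to +14 at 20 per arm.

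**Other readings of the GEE response.**

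- Post-meal values: 75–76% power against 79/88/99% adjusted, at every k. The variance cut is ρ²/0.8 = 11/31/61%.
- All four values: 53–69% power against 79–99%. The meal coefficient averages three shifted values and one unshifted value, so it estimates only 3/4 of the post-meal difference.

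**Chance imbalance.** At 12 per arm the SD of the baseline difference between two arms is √(2/12) = 0.41 baseline SDs, so a 2-SE gap is 0.82. The change contrast then shifts by (c − 1) × 0.82; with k = 1 and ρ = 0.3 this is −0.57. Given such a gap, with the third arm midway, Mann-Whitney after a significant Kruskal-Wallis gives 7.2/5.8/4.7% false positives at k = 1 and 2.2–4.5% at k = 1.5–2. This effect is small.

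**When adjustment does not help.**

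- If all slopes equal 1, variance relative to change rises 3% at 12 per arm.
- If the meals have slopes 1, 1 and 0 (residual SD 0.7), the common slope is 2/3. The contrast between the two slope-1 meals has a large-sample variance ratio of (0.49 + 1/9)/0.49 = 1.23. At 12 per arm it rises 28%, while the other two contrasts fall 20%. A centred baseline-by-meal term cuts the 28% to 7%.
- With slopes 0.8/0.6/0.4, all three contrasts gain (10/20/29% lower variance).

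**Small-sample reference.** At 12 per arm an uncorrected sandwich z test rejects 7.3–8.1% under the null with baseline and 6.9–7.7% without. The model-based t test on the adjusted contrast rejects 4.6–5.0% with normal, lognormal or t(3) data and a common slope.

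**The case against.** The strongest reply is that nothing here is wrong. A change outcome already uses baseline, the tests are valid, and the authors deliberately chose rank methods: "All the statistical analyses will be based on non-parametric tests". Adjustment would alter only a sensitivity analysis and gives the primary test no extra power. The three-day diet and 12-hour fast should narrow baseline spread, which favours the k = 1.5–2 rows, where the gain over change is at most 5 points and mostly nil. The GEE sentence also looks like shorthand: it omits time as well, and a random effect is not a component of a GEE. Silence on baseline is then weak evidence that it was excluded on purpose.

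Much of this stands. It is a matter of efficiency, the gain over change may be nil, and every percentage is assumed. Heavy tails also favour the rank tests: with t(3) data, ρ = 0.5 and k = 1.5–2, Kruskal-Wallis on change beat linear ANCOVA by about 9 points. The meals may also have different slopes; the protocol itself says "While other nutritional values/components varied across groups".

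It does not remove the point. The plan never says the GEE is run on change, and under either other reading the loss is not limited to the small gains. The model is already planned and the covariate already collected. Specifying both in advance settles the ambiguity and avoids a choice made after seeing the data.

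**Conclusion.** The point holds: no planned between-meal analysis uses fasting EAA as a covariate. This is a minor, optional improvement in precision and does not correct an invalid test. Under the assumed inputs, adding baseline changes power by −1 to +20 points against a GEE on changes, with the upper end requiring equal SDs and ρ = 0.3. Against a GEE on post-meal values the gain is +3 to +23 points. With a slope common to the meals, the adjusted contrast is in large samples at least as precise as either alternative; with meal-specific slopes that is not guaranteed. Confidence in the size is medium, because sample size, SDs and correlations had to be assumed.

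**What to change.** 1. Keep Kruskal-Wallis and Mann-Whitney as the main analysis, and state that they are run on change from baseline at 30, 90 and 180 minutes.
2. Specify the sensitivity GEE with the three post-meal values as responses and baseline not among them. Include the participant's baseline value of that EAA as a covariate, with meal, time, meal-by-time and baseline-by-time terms.
3. Report the Mankai–cheese and Mankai–peas contrasts with a small-sample t reference. With complete data, a linear model on participant means (or at each time point) with meal and baseline gives the same contrasts and a t test directly.
4. As a check on unequal slopes, refit with baseline centred at its overall mean and a baseline-by-meal term.
5. Analyse B12 and the other biomarkers the same way without time terms. This reads "Other parameters will be measured only in 3 hours interval" as sampling at baseline and 3 hours.
6. If the non-parametric rule must hold throughout, Quade's rank ANCOVA is an adjusted alternative.

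The cost is SAP wording and no new data. Each contrast loses about one degree of freedom. The whole model estimates three baseline slopes over time, and the unequal-slope check adds two more parameters to a time-averaged contrast. With heavy tails a linear model can lose up to about 10 points of power against Kruskal-Wallis, and Quade's test about 3, so the adjusted model should accompany the rank tests and not replace them.
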